2.5 Intervention methods

2.5.1 Control group:

2.5.1.1 Paramedics: Composed of 30 female caregivers aged between 23 and 40 years who have previously received training in the standard of care for the relevant surgical perioperative but have not yet been specially trained in the non-pharmacological intervention-cartoon nurse-patient interaction mode.

2.5.1.2 Preoperative care: The responsible nurse introduces the hospital room environment and preoperative preparation to the child and parents, and the child and parents are familiar with the environment and the preoperative preparation process. The responsible nurse is always available to answer questions.

2.5.1.3 Postoperative routine care: including monitoring of vital signs, maintaining the acid-base balance of water and electrolytes, lung care, pipeline care, basic care, etc.

2.5.1.4 Postoperative pain management: (1) Pain assessment: First, the caregiver will

evaluate the child's pain level regularly (every 4 hours) using the Child Pain Rating Scale (Wong-Baker scale). (2) Non-pharmacological management of pain: When the child cries due to pain, the caregiver uses conventional non-pharmacological intervention and comfort methods such as hugging, coaxing, and touching. (3) Pain drug management: 1~3 days after surgery: pain is most severe within 24~72 hours after surgery, and may last for several days or weeks in some children. Children are routinely given oral or intravenous analgesics after surgery, usually for 3 consecutive days (see table 4 for details). Table 4 Analgesic usage and dosage Version number: 1.1 Version date: 2024.7.11 5

Type	Usage	Interval	Time	Maximum daily dose	Ibuprofen suspension	Orally	4-6 h within 24 hours	no more than 4 1-3 years old, weight 10-15kg, 4ml	4-6 years old, body weight 16-21kg, 5ml	7-9 years old, body weight 22-27kg, 8ml	ibuprofen injection once (6 months to less than 12 years old)	Intravenous infusion 10mg/kg 4-6 h 2.4g or 40mg/kg (whichever is lower)	Maximum single dose 400mg	Before administration, it must be diluted, concentration \leq 4mg/ml acetaminophen oral suspension orally 4-6 hours within 24 hours no more than 4 1-3 years old, weight 12-15kg, once 3ml	4-6 years old, body weight 16-21kg, once 5ml	7-9 years old, weight 22-27kg, once 8ml	After 3 days of surgery: can be administered as needed according to the results of pain assessment.
------	-------	----------	------	--------------------	----------------------	--------	-----------------------	---	---	---	---	---	---------------------------	--	--	---	---

Pharmacological treatment is considered when the child presents with moderate to severe pain (Wong-Baker score ≥ 4) and non-pharmacological interventions do not provide adequate relief. Doctors will decide which drugs to use, including NSAIDs or weak opioids, based on the child's overall condition and the parent's opinion. Once the decision to use medication is made, the caregiver will administer it as directed and monitor the child's pain relief and any potential adverse drug reactions.

2.5.2 Intervention group:

2.5.2.1 Establish a research team: A total of 7 team members, including 1 nursing graduate tutor, 1 pediatric intensive care unit doctor, 1 pediatric intensive care unit nurse, 1 pediatric intensive care unit specialist nurse, 2 pediatric intensive care unit nurses, and 1 psychological counselor (the researcher himself). (1) Determine the team leader and responsibilities: The nursing graduate supervisor and researcher are responsible for the preliminary research of the study, literature review, literature screening, intervention plan formulation and training, schedule control arrangement, research quality control, personnel management, task allocation, coordination of various work, and final result analysis. (2) Clarify the responsibilities of group members: doctors are responsible for providing medical knowledge and answering medical questions raised by children and parents; The head nurse is responsible for guiding routine nursing-related work and assisting the principal investigator to control the overall research progress and quality of research. 1 specialist nurse recruited the children and

implemented the intervention; 2 nurses are responsible for the collection of clinical case data; 1 psychological counselor is responsible for participating in research and psychological guidance.

2.5.2.2 Intervention program training: Nursing is carried out by the same group of caregivers as the control group, but the researcher completes the implementation plan and data collection method training of the cartoon-based nurse-patient interaction model during the interval period before the intervention group implements the study.

2.5.2.3 Establishment of animation database: The research team established a database of animations before the implementation of the intervention group. First of all, a cartoon database is established based on the cartoons that most preschool children love, including "Bear Infestation", "Cute Chicken Squad", "PAW Patrol Achievements", "Peppa Pig", "Sheep and Gray Wolf", "SpongeBob SquarePants", "Pig Man", "My Little Pony", "Little Princess Sophia", "Undersea Column", "Tom and Jerry", "Bidden Rabbit", "Pig Man", "Super Wings Pan", "Milk Dragon", "Elf Dream Ye Luoli", etc., these vivid and interesting cartoons can have a benign effect on the mood and condition of the child. Download it to your phone or iPad.

2.5.3 Pre-trial In September 2024, 5 children with CHD who met the criteria for inclusion were selected at Beijing Children's Hospital Affiliated to Capital Medical University for pre-experiment to observe the feasibility of the intervention method.

3. Research period 2024.8.1-2024.12.31

4. Subject selection Inclusion criteria: (1) According to the "Guidelines for the Diagnosis and Treatment of CHD in Children" and cardiac ultrasound imaging [100] Children diagnosed with CHD for surgical treatment; (2) Age 3~7 years old, including 3 and 7 years old; (3) The surgical method is thoracotomy; (4) Diagnosis of ventricular septal defect, atrial septal defect or atrial septal defect combined with ventricular septal defect, patent ductus arteriosus, tetralogy of Fallot; Exclusion criteria: (1) Those with obvious abnormal cardiovascular lung, liver and kidney function, other chronic diseases, neuropsychiatric diseases, and malignant tumors; (2) Congenital heart disease combined with other organ malformations; (3) taking sedatives and antidepressants; (3) Those with intellectual disability, developmental delay, or behavioral disorder; (4) Hearing and communication impairments in children; (5) Parents of children with mental retardation or mental illness; Removal criteria: (1) Extubation cannot be done after surgery; (2) Unplanned reoperation 48 hours after surgery; (3) Unable to communicate normally due to impaired consciousness or changes in condition after surgery; (4) Those who stop treatment due to other reasons such as transfer to hospital, department or death midway. (5) Children and their families choose to withdraw from the study midway for

various reasons.

4. Research methods

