2.1 Research subjects Children who underwent CHD surgery in the Children's Cardiac Intensive Care Unit (CCU) of Beijing Children's Hospital Affiliated to Capital Medical University from June 2024 to November 2024 were selected according to the convenient sampling method. 2.2 Grouping methodology: To ensure the ethics of the study and the feasibility of implementation. In view of the moral and interference that may arise between different non-pharmacological interventions in two groups of children in a practical clinical setting, affecting the emotions of children and health care providers, this study will adopt a phased control approach. Children in June-July 2024 were the control group and the intervention group in October-November 2024.

2.3 Sample size calculation In this study, the sample size calculation formula $N1=N2=2\times[(Z\alpha+Z\beta)\sigma/\delta]^2$ was used to estimate the sample size using the Wong-Baker scale score

as the main utility index. Consulting relevant literature [101], it was found that $\sigma=0.91$, $\delta=0.47$, the test level was $\alpha=0.05$ (two-sided), the grasp was $\beta=0.1$, and the t-cut-off value table showed $Z\alpha=1.96$ and $Z\beta=1.282$. Considering the loss to follow-up of the samples during the study, the calculated sample size was increased by 10%, and finally $N \approx 86$ was obtained, with 43 cases in each of the intervention and control groups.

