4.1 Implementation of the intervention program

4.1.1 Preoperative care: The children in the intervention group completed the following preoperative interactions on the basis of the preoperative routine care in the control group. (1) Choose cartoons: Because each age group or even 1 year apart children like different cartoons, and considering the different personality and psychological characteristics of children, each child likes different cartoons. When using cartoons, it is difficult to ensure that cartoons are at the same level of attraction to children and that every child's attention is devoted to the cartoon. Therefore, the caregiver determines the favorite cartoon of each child before surgery. The preoperative nurse in charge and the parents of the child to understand the children's favorite cartoons, and together with the family members, let the children choose 3 favorite cartoons in the cartoon database, and the responsible nurse will record the names selected for postoperative application. (2) Interaction between the nurse and the child: take the child as the leader, communicate with the child before surgery, and the responsible nurse patiently guides the child to raise his or her concerns about the operation, and uses easy-to-understand friend-style communication to alleviate the child's anxiety and fear of surgery. (3) Interaction between nurses and parents: The responsible nurse distributes the "Disease Manual", which details the pathogenesis, symptoms, treatment, surgical steps and postoperative precautions. In order to reduce the anxiety of parents of children and allow parents to fully express their psychological state before surgery and their worries about surgery, the nurse answered the parents' questions and concerns in detail. The responsible nurse and parents discuss specific measures for postoperative care, and affirm and encourage the active participation of parents. (4) Parent-child interaction: Teach parents how to interact with children. Parents can use positive language to guide and encourage their children to face and receive surgery. Reduce the impact of parents' anxiety about the child's surgery, face the child with a smile, hug the child, and choose cartoons to watch before and after the operation.

4.1.2 Postoperative routine care: After returning to the CCU to remove the endotracheal tube, the children will receive routine postoperative care in the control group.

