10. Data security monitoring All collected data will be stored and analyzed uniformly to strictly protect the privacy of participants. To ensure the accuracy of the data and the reliability of the research, we will also conduct regular audits of data quality. All reviews and entries are entered by the researcher into the same computer electronic data record form file. All questionnaires are collected and checked by the survey staff on the spot, and after the survey, the researcher reviews the collected questionnaires and eliminates invalid questionnaires.

11. Statistical processing The data were entered by excel2023 software and a database

was established, and SPSS29.0 was used to perform statistical analysis on the data. The data that meet the normal distribution are expressed by mean \pm standard deviation, and the data that do not meet the normal distribution are statistically described by the median and interquartile spacing M (IQR). The counting data are described by composition ratio and percentage. For statistical inference, paired t-tests were used for intra-group comparisons of normally distributed and homogeneous variance, and two-sample t-tests were used for comparisons between groups. The correction t-test is used for uneven variance; The counting data were tested by chi-square. All statistical tests were two-tailed tests, with a $P<0.05$ indicating that the difference was statistically significant.

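### Convenience sampling, with the group known in advance and no screening log, leaves room for undetected differential selection between the two phases

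*Combined protocol and SAP*

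**What the plan says.** - **Sampling (2.1).** Children having surgery for congenital heart disease in one cardiac intensive care unit "were selected according to the convenient sampling method". No section requires that eligible children be approached consecutively.
- **Allocation (2.2).** "Children in June-July 2024 were the control group and the intervention group in October-November 2024".
- **Recruitment (2.5.2.1).** In the team's task list, "1 specialist nurse recruited the children and", the sentence continuing after a page break, "implemented the intervention; 2 nurses are responsible for the collection of clinical case data". The list stands under the intervention-group heading. No section says who recruited the controls.
- **Delivery (2.5.2.2, 4.1.1, 4.1.3).** "Nursing is carried out by the same group of caregivers as the control group", and the responsible nurse handles cartoon choice, preoperative interaction and playback. The specialist nurse is therefore not shown to be the only person delivering.
- **Eligibility (section 4, Subject selection).** One list serves both phases. It excludes, among others, "Those with intellectual disability, developmental delay, or behavioral disorder".
- **Appeal of the intervention (4.1.1).** The plan accepts that "it is difficult to ensure that cartoons are at the same level of attraction to children".
- **Analysis (section 11).** "two-sample t-tests were used for comparisons between groups", with a corrected t-test for unequal variances and chi-square for counts. No baseline covariate is named.
- **Not found anywhere:** a screening or refusal log, an enrolled fraction by phase, or a recruiter separate from delivery.

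**The concern.** With the group set by the month, every decision to approach a child or to consent is made knowing what the child will receive. In October-November there is a reason to favour children who seem likely to engage with a cartoon, and a parent who dislikes screens has a reason to decline. Neither cartoon-specific reason exists in June-July. Other selection, such as approaching easier families or losing reluctant ones, can happen in both phases and matters only if it differs between them.

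If the children who enter the intervention phase would have scored lower on Wong-Baker anyway, the group difference contains that gap as well as any effect of the cartoons. Child anxiety (mYPAS) and parent satisfaction, also listed in section 6, could be affected in the same direction. Without a record of who was eligible, approached and refused, a reader of the results cannot tell how much of a difference arose in this way.

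**Working it through.** **Inputs from the plan (2.3).** SD 0.91 and target difference 0.47 on Wong-Baker; two-sided alpha 0.05; 43 per group.

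**The plan's own figure.** 2 × [(1.96 + 1.282) × 0.91 / 0.47]² = 78.8 per group, and 78.8 × 1.10 = 86.7. The plan treats 86 as the total and halves it to 43. That is a separate matter; 43 is used below only because it is the stated group size, and the mean shifts do not depend on it.

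**Assumptions (the plan gives no figure for selection).** Scores are normal. In the intervention phase only, a fraction p of eligible children, those least favourable on some trait, is left out. The trait has correlation r with the later pain score.

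**Formula.** Removing the top fraction p of a standard normal trait lowers its mean by φ(z)/(1 − p), where z is the upper-p cut-off. The pain mean falls by r × 0.91 × φ(z)/(1 − p).

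- p = 0.10: 0.1755 / 0.90 = 0.195
- p = 0.20: 0.2800 / 0.80 = 0.350
- p = 0.30: 0.3477 / 0.70 = 0.497

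| Left out | r = 0.2 | r = 0.5 | r = 1 (upper bound) |
|---|---|---|---|
| 10% | 0.04 | 0.09 | 0.18 |
| 20% | 0.06 | 0.16 | 0.32 |
| 30% | 0.09 | 0.23 | 0.45 |

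For example, 0.5 × 0.91 × 0.497 = 0.226. As a share of 0.47, the range for r = 0.2-0.5 runs from 0.0355/0.47 = 8% to 0.226/0.47 = 48%.

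**Effect on the test if the true effect is zero.** The standard error at 43 per group is 0.91 × √(2/43) = 0.196, so a difference of 1.96 × 0.196 = 0.38 is significant. With a shift b, the two-sided rejection probability is Φ(−1.96 − b/0.196) + 1 − Φ(1.96 − b/0.196):

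- b = 0.04 (unrounded 0.0355): 5.4%
- b = 0.10: 8.0%
- b = 0.20: 17.5%
- b = 0.23 (unrounded 0.226): 21.0%

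The nominal rate is 5%. The slight loss of variance caused by selection is ignored.

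**Safeguards set against the gap.** The shared eligibility list limits who can enter, but does not decide which eligible children are approached. Using the same caregivers in both phases standardises care, not enrolment. The two data nurses act after enrolment. The t-test has no covariates.

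**The case against.** **The text does not show choice being exercised.** Section 2.1 does not say that the nurse picks among eligible children; it could mean every available case at one site. No surgical volume is given, so finding 43 children in two months may leave little room to choose. This stands: the documents show that selection is possible and would go unseen, not that it occurred.

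**The recruiter is not the sole deliverer.** This also stands. The dual role is stated, but for one nurse among several and only in the intervention-group section. The silence about control recruitment leaves open a difference between phases; it does not establish one.

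**A reader might infer that selection alone would produce the planned effect.** By the formula above, leaving out about 31% of children would reproduce nearly the whole 0.47, but only if an impression before surgery predicted pain after it perfectly. Nothing in the documents supports r = 1. Even r = 0.5 with 30% left out gives 0.23, below the 0.38 needed for significance, so the expected result is an inflated false-positive risk and not a wholly spurious finding.

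**A reader might also infer that no analysis could help.** The documents do not support that. Section 6 lists mYPAS; if taken before surgery it could be a partial proxy for temperament. Its timing is not stated, however, and section 11 plans no adjustment.

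**The phased design has a stated rationale (2.2),** and better enrolment does not cure calendar confounding. Both are true, but neither is a reason to leave enrolment unrecorded.

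**Conclusion.** The point holds as a gap in enrolment control. Convenience sampling, a group known from the month, and a recruiter who also implements in the intervention phase leave differential selection neither prevented nor visible, and the planned unadjusted comparison would not correct it.

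Its size cannot be derived from the documents. Under the assumptions above, the shift is about 0.04-0.23 points, or 8-48% of the target difference, with a false-positive risk of roughly 5-21% in place of 5%. The r = 1 figures, 0.18-0.45, are an upper bound only. The direction, in favour of the intervention, is plausible but also assumed: nothing in the documents links reluctance about screens to higher pain scores. The change should be made because it is cheap and is what would let the sponsor show that selection was small.

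**What to change.** 1. **Section 2.1.** Replace convenience sampling with consecutive approach, in order of surgery date, of every child who meets the criteria in section 4 (Subject selection), under the same rule in both phases.
2. **Screening log.** For each phase, record eligible, approached, refused, reason, age and diagnosis. Report the enrolled fraction by phase.
3. **Controls already enrolled.** Rebuild the list of eligible children from the surgical schedule, compare enrolled with non-enrolled children on age and diagnosis, and state that approach and refusal may not be recoverable. State also who recruited the controls and how: June-July precedes the research period in section 3, which begins on 1 August 2024.
4. **Section 2.5.2.1.** Where practical, have an existing team member who neither delivers the intervention nor collects outcomes approach families. Moving the task to a data-collection nurse would join recruitment to data collection. Whoever recruits will still know the group from the month, so items 1 and 2 do the main work.

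**Cost.** A wording amendment and a little logging, with no extra staff. The apparent effect may be smaller. If the controls were not consecutive, an asymmetry between phases remains and should be reported. Confounding by calendar period is untouched.

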postoperative pain management practice of clinical children. (2) Optimization of treatment plans: The study will explore whether cartoon-based nurse-patient interaction models can help improve children's treatment adherence, reduce complications, stabilize hemodynamic indicators (children's heart rate, blood pressure, respiratory rate, oxygen saturation, arterial blood gases), and shorten hospital stay. These are important indicators for evaluating the merits and demerits of drug labor pain treatment regimens, and have important reference value for optimizing the treatment plan for heart disease in children. (3) Improve the psychological state of family members: The psychological state of the parents of the child directly affects the rehabilitation process of the child and the overall health of the family. Non-pharmacological nursing intervention - cartoon-based nurse-patient interaction model can effectively improve the psychological state of parents and help improve parent satisfaction. (4) Improving the quality of care: This study will also evaluate the impact of non-pharmacological nursing interventions, cartoon-based nurse-patient interaction models, on the quality of caregiver work, and explore how to improve the quality of nursing services through these interventions, thereby improving the overall satisfaction of children and caregivers. Overall, this study will not only help enrich and expand the scientific research data on the nurse-patient interaction pattern of non-pharmacological nursing intervention-cartoons, but also provide new perspectives and methods for clinical practice, especially in the special population of pediatric CHD. Through the method of empirical research, the progress of knowledge and the improvement of practice in related fields should be promoted.

3. Research design types, principles and test steps

1. Study design 1. Study design: Interventional controlled study.

2. Research Methodology:

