4.1.3 Postoperative pain management: On the basis of postoperative pain management in the control group, the responsible nurse uses a mobile phone or Ipad to play the cartoons selected by the child before surgery according to the child's choice, and can watch the cartoon throughout the whole process or according to the child's wishes after waking up after the operation, and the volume of the device is adjusted to a comfortable

level, each cartoon does not exceed 30 minutes, 3~6 times a day, to distract attention and let the child's eyes rest to protect vision. Nurses can also discuss the plot with the child, mobilize the child's subjective initiative, gain their trust, and change from passive participation to active participation.

5. Concomitant medication None

6. Observation indicators General information, physiological indicators, postoperative complications, pain assessment, children's anxiety assessment (mYPAS score), anxiety assessment, parent satisfaction.

7. Pre-assessment of project risks and risk disposal plan In this study, the use of electronic products such as mobile phones or IPAPs may cause visual fatigue and dependence in children.

8. Quality control and quality assurance of research The quality control and supervision of research are explained from the aspects of laboratory index testing, implementation of relevant SOPs, researcher training, subject compliance, and research monitoring.

8.1 Researcher training Nursing is carried out by the same group of caregivers as the control group, but before the intervention group implements the study, the researcher completes the implementation plan and data collection method training of the cartoon-based nurse-patient interaction model during the interval.

8.2 Subject compliance Before participating in the trial, the investigator should explain the potential risks of using this study to all subject guardians and inform the subjects that cooperating with the safety monitoring required in the trial protocol can minimize the risks.

9. Data preservation The collected research data is entered on the same day, and the researcher enters it by one person, with double data entry and regular data cleaning to minimize human error. At the same time, use a secure, encrypted electronic data system to protect participant information.

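### The removal criteria can take children with serious postoperative events out of the complication comparison, and no stated analysis set keeps them in

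*Combined protocol and SAP*

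**What the plan says.** All references are to the combined protocol and SAP.

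- **Removal.** Section 4 (Subject selection) has a list separate from the exclusion criteria. It opens "Removal criteria: (1) Extubation cannot be done after surgery; (2) Unplanned reoperation 48 hours after surgery". The next two items read "3) Unable to communicate normally due to impaired consciousness or changes in condition after surgery" and "4) Those who stop treatment due to other reasons such as transfer to hospital, department or death midway". The fifth is withdrawal by the child or family.
- **Timing.** Consent is taken when the sample is selected (section 2.4). Section 4.1.1 starts the intervention before surgery: "The children in the intervention group completed the following preoperative interactions on the basis of the preoperative routine care in the control group". Section 4.1.2 places the next stage after extubation: "After returning to the CCU to remove the endotracheal tube, the children will receive routine postoperative care in the control group".
- **Complications as an outcome.** Section 2, item (2), asks whether the model can help "reduce complications, stabilize hemodynamic indicators". Section 6 lists "General information, physiological indicators, postoperative complications, pain assessment" among the indicators. No definition, event list or time window is given.
- **Population and analysis.** Section 2.1 selects "Children who underwent CHD surgery". Section 2.2 makes June-July 2024 the control period and October-November 2024 the intervention period. Section 11 plans t-tests for continuous data and chi-square for counts, and names no analysis set. The only other rule for dropping data is in section 10, which discards invalid questionnaires.
- **Allowance.** Section 2.3 adds 10% for loss to follow-up and plans 43 children per group, with the Wong-Baker score as the main measure.

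**The concern.** The removal list works on children already in the study, and four of its triggers (inability to extubate, unplanned reoperation, impaired consciousness, death) are events that a complication table would normally be expected to show. If removal means leaving the analysis, children leave the complication comparison because they had a complication. The 10% allowance replaces head-count. It does not put the events back.

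The groups are successive calendar periods without randomisation, so nothing in the design makes removals equal between them. Unequal removal could hide a benefit, hide a harm, or create an apparent difference where there is none. What is at stake is mainly the reported complication rates and whether serious events can be seen by group. The pain comparison is less exposed.

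**Working it through.** **1. Order of events.** Consent comes at selection, then the preoperative interaction in the intervention group, then surgery. Criteria (1) to (3) are postoperative by their own terms. The list therefore acts after enrolment and, in the intervention group, after the intervention has begun.

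**2. The plan's own figures.** The plan gives no complication or removal rate to reproduce. Its only computed figure is the sample size. The formula in section 2.3 gives 2 × [(1.96 + 1.282) × 0.91/0.47]² = 78.8 per group, and × 1.1 = 86.7. The stated 43 per group is about half of that. That is a separate matter; 43 is used below only as the stated denominator. The 10% allowance within it is 43 − 43/1.1 = 3.9, about 4 children per group.

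**3. Effect on complications. All event counts are assumptions.** Rate with every child kept = events/43. Rate after removal = (events − removed)/(43 − removed). Totals are fixed at 4/43 = 9.3% (control) and 7/43 = 16.3% (intervention), a difference of 7.0 points.

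| Removal-type events, control v intervention | After removal | Difference (points) | Share lost |
|---|---|---|---|
| 1 v 1 | 3/42 v 6/42 | 7.1 | none |
| 1 v 2 | 3/42 v 5/41 | 5.1 | 28% |
| 1 v 3 | 3/42 v 4/40 | 2.9 | 59% |
| 1 v 4 | 3/42 v 3/39 | 0.5 | 92% |

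Exchanging the groups gives the same sizes with the opposite sign. Three further cases mark the range:

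- Equal removal, 4 v 4, with 4 other events in each group: 8/43 v 8/43 (18.6% each) becomes 4/39 v 4/39 (10.3% each). The difference stays at zero, but both rates are understated.
- Removal 4 v 0, with 6 other events in each group: 10/43 v 6/43 (−9.3 points) becomes 6/39 v 6/43 (−1.4 points). A difference is hidden.
- Removal 0 v 4, with other events 6 v 2: 6/43 v 6/43 (no difference) becomes 6/43 v 2/39, or 14.0% v 5.1% (−8.8 points). A false benefit appears.

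With every child kept, 4/43 v 7/43 has p = 0.33 by uncorrected chi-square.

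**4. Effect on pain.** The bias in the group difference has size (difference in removal rates) × (mean pain of removed minus retained children). Assume a gap of 1 SD = 0.91 (section 2.3) and removal rates 5 to 10 points apart: 0.05 × 0.91 = 0.046 and 0.10 × 0.91 = 0.091. Against δ = 0.47 that is 10% to 19%. The standard error is 0.91 × √(2/43) = 0.196, so it is 0.23 to 0.46 of a standard error. It is zero if removal rates and pain gaps are equal in both periods.

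**5. Can the remedy itself bias?** Yes, if events are found more completely in one period. Assume 7/43 in both groups, 3 of them removal-type, with the control ones unlogged: 4/40 = 10.0% v 7/43 = 16.3%, a false harm of 6.3 points. Both periods need the same source.

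**The case against.** The other side has several good points.

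- **Discard is inferred.** Removal could mean only that pain and anxiety follow-up stops. This stands as a limit. But a list of removal criteria under subject selection, with no analysis set anywhere, is most naturally read as taking children out of the comparison. If the sponsor means otherwise, one sentence settles it.
- **Complications are undefined.** Whether failed extubation or reoperation would be counted is not stated. This stands too, so the claim is that they are plausibly complications, and the fix has to include an event list.
- **Criteria (1) and (3) serve a purpose.** A child who is never extubated does not reach the postoperative cartoon stage, and a child who cannot communicate may have no valid Wong-Baker score. This is a sound reason for the pain comparison. It does not carry over to complications, which need no self-report.
- **Using pre-removal pain scores as the main analysis could add bias.** Section 2.5.1.4 says pain is worst at 24 to 72 hours, and no summary time point is set. If truncation shifts a child's value by 1 SD and removals are 4 v 1, the bias is 3/43 × 0.91 = 0.063 points, as large as the effect it would correct. This stands, so such scores belong only in a sensitivity analysis.
- **The sizes are assumed.** The large distortions need unequal removal, of which the documents give no evidence.

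A reader might infer that the plan orders deaths and reoperations to be deleted, or that the pain result is invalid. The documents support neither: they do not say what happens to removed children's data, and removal for want of a score is defensible.

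**Conclusion.** The point holds in limited form. The plan removes enrolled children for events that are plausibly complications, makes complications an aim and an indicator, and states no analysis set that keeps those children. On the natural reading, serious events drop out of a comparison between two non-randomised periods.

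The distortion of the difference may be nil when removals are equal, and in the assumed cases reaches about 9 percentage points in either direction when they are not. Every rate behind those figures is an assumption. It would be too strong to say that a test result will change: the assumed 4/43 v 7/43 is far from significance even with every child kept. The issue is accurate rates and visible serious events. For the main pain measure the possible bias is under half a standard error on the assumptions shown, and does not call for a different primary comparison.

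The plan should be changed. Confidence is medium, because both the discard and the classification of events are inferred.

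**What to change.** 1. **Complications.** Compare them in all enrolled children who had surgery, by period group, with the planned chi-square test. Count removal events that are complications (inability to extubate, unplanned reoperation, impaired consciousness, death) as events. Use one written event list, with its time window, for both groups, and say how transfers and other changes in condition are treated. After withdrawal, use data only as far as consent allows.
2. **Ascertainment.** Find these events from the same source, the medical records, in both periods. If control-period removals cannot be recovered, say so and do not interpret the difference as an effect.
3. **Reporting.** Give the number removed by group and criterion.
4. **Pain.** Keep the planned comparison. State the number of children without usable scores in each group. Use scores recorded before removal only as a sensitivity analysis.
5. **Clarification.** The sponsor should state whether criterion (2) refers to reoperation within or after 48 hours; the wording may be a translation effect.

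Cost: one paragraph on analysis sets, an event list, a removal table, one sensitivity analysis and a small amount of record review. The planned tests and clinical care are unchanged. The main uncertainty is the control period: the documents do not say whether removed children were logged. Because the plan's version date (2024.7.11) falls inside that period, the event list would be written after some control data existed, so it should be fixed before the groups are compared.
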